***Data Safety & storage:***

The main risk to subjects is the accidental release of PHI. Careful record management methods will be in place to ensure this type of privacy breach does not occur.

*Subject ID Key:* Each subject will be given a unique subject ID number. A subject ID key will be used to match the subjects Financial Identification Number (FIN). The subject ID key, linking the subject ID numbers to the FIN will be kept in a password-protected file on the pharmacy IV room and pharmacy co-investigator computer. Only the research team (PI, sub PI and research pharmacists) will have access to this information, and they will not disclose this information to any other person or entity. The subject ID key will be destroyed as soon as possible after the data set has been completely abstracted and validated for accuracy and completeness.

*Data set:* Similarly, the data set will be kept in a password-protected file and stored separately from the

subject ID key in the locked office of the study coordinator. Only the research team will have access to this information, and they will not disclose this information to any other person or entity. Three years after the completion of the study, all collected data will be destroyed by permanently deleting electronic copies.

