study in 24 patients with severe sepsis and septic shock. [23] In this study patients were randomized to placebo (n=8), low dose intravenous vitamin C (50 mg/kg) (n=8) or high dose vitamin C (200mg/kg). Vitamin C attenuated the inflammatory response with both doses of the vitamin being devoid of any side effects. Although the Sequential Sepsis Related Organ Failure Score (SOFA) fell significantly in both treatment arms the study was underpowered to determine any outcome benefit. Zabet and colleagues performed a RCT in which they evaluated the role of intravenous vitamin C in a dose of 100 mg/kg/day (about 7g/day) in 28 surgical ICU patients with septic shock. [24] In this study the mean dose of norepinephrine and duration of norepinephrine administration were significantly lower in the ascorbic acid than the placebo group. The 28-day mortality was significantly lower in the ascorbic acid than the placebo group (14% vs. 64%, p = 0.009). No side effects related to the vitamin C infusion were reported. Tanaka et al randomized 37 patients with severe burn to very high dose vitamin C (about 110g/day) or placebo.[25] Patients who received vitamin C required less fluid resuscitation with a trend towards reduced length of stay and mortality. No adverse effects were noted with the very high dosages of vitamin C. Several studies have administered vitamin C in doses exceeding 100g/day as adjuvant therapy in patients with cancer with no discernable side effects. [26-33] Vitamin C appears to be toxic to normal human cells (not cancer cells) at a concentration on greater than 25 mM. [33] A dose of 6g/day will achieve a steady state serum concentration of about 240uM [34-36] which is about 100 times less than the dose required to cause cellular toxicity. The package insert for vitamin C [37] lists no contraindications or adverse effects of the drug and states that as much as “6 grams has been administered without evidence of toxicity”. The only reported restriction to the use of high dose intravenous vitamin C is in patients with known glucose-6-phosphate deficiency (G6PD) in whom hemolysis has been reported. [38,39] It is important to recognize that patients with sepsis predictably have very low serum vitamin C levels, which can only be corrected with intravenous vitamin C in a dose of more than 3gm per day. [23,34,36] The low or undetectable levels of vitamin C likely result from the metabolic consumption of the molecule as well as increased renal losses. Furthermore, unlike all other mammals, primates and guinea pigs are unable synthesize vitamin C is due to mutations in the L-gulonolactone oxidase (*GLO*) gene which codes for the enzyme responsible for catalyzing the last step of vitamin C biosynthesis. [40] In almost all species, except humans and guinea pigs, vitamin C production increases during stress and is secreted by the adrenal gland; in these species vitamin C is best considered a stress “hormone”. [40] Vitamin C is an essential cofactor for the production of corticosteroids and catecholamines by the adrenal gland. [13,41] Vitamin C has been shown to reverse adrenal suppression caused by induction doses of etomidate during anesthesia.[42,43]

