
Ascorbate donates a single electron in all its redox reactions, generating the ascorbate radical. This radical is not very reactive with anything but itself. Dismutation of two ascorbate radicals forms a molecule each of ascorbate and dehydroascorbate. Hydrolysis of the lactone ring of dehydroascorbate

irreversibly converts it to 2,3-diketo-1-gulonic acid which is then converted to oxalate. Oxalate is normally excreted by the kidney and serum levels will increase with renal impairment. In patients with renal impairment receiving mega-dose vitamin C, supersaturation of serum with oxalate may result in tissue deposition as well as crystallization in the kidney. [44,45] Glyoxylate, a byproduct of intermediary metabolism, is either reduced to oxalate or oxidized to CO2 by the enzyme glyoxylate aminotransferase; thiamine pyrophosphate is a co-enzyme required for this reaction. [46] Thiamine deficiency increases the conversion of glyoxylate to oxalate resulting in hyper-oxalosis. [47,48] Donnino and colleagues have demonstrated that thiamine deficiency is common (32%) in patients with sepsis and that treatment with thiamine in these patients reduces mortality. [49] In a post-hoc analysis of this study these authors demonstrated that thiamine decreased the risk of acute kidney injury and the required for renal replacement therapy in all treated patients. [50]

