**Study end-points:**

***Primary end-point***

- i. Time to vasopressor independence. Defined as the time from starting the active treatment/placebo to discontinuation of all pressors
- ii. Delta SOFA score, defined as the initial SOFA score minus the day 4 SOFA score

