## **Vitamin C, Hydrocortisone and Thiamine dosing protocol and randomization**

### ***Medication dosing.***

Based on published clinical data, vitamin C pharmacokinetic modeling, the package insert as well as the preliminary study by Marik et al, Vitamin C will be administered as an intravenous dose of 6gm per day divided in 4 equal doses. [22-24,34-37] This dosage is reported to be devoid of any complications or side effects. Hydrocortisone will be dosed according to the consensus guidelines of the American College of Critical Care Medicine.[52] Thiamine will be administered according to current recommendations in a dose of 200mg q 12 hourly. [69]

This is a double-blind placebo controlled study. Only the dispensing pharmacist will be aware of the treatment allocation. Patients will be randomized to receive either vitamin C/hydrocortisone/thiamine or triple placebo using a random number table provided to the dispensing pharmacists. Each patient will be allocated a unique subject ID which will be linked to the randomization sequence. Only the dispensing pharmacists will have a record of the subject ID and randomization sequence. The vitamin C, vitamin C-placebo, hydrocortisone, hydrocortisone-placebo, thiamine, and thiamine-placebo will be formulated as follows:

***Vitamin C:*** Vitamin C is provided by the manufacturer as a 50 ml vial at a concentration of 500mg/ml. Three (3) ml of vitamin C will be placed in a 50 ml bag of Normal Saline (1500 mg vitamin C in 50ml bag) which will then be infused over 30 minutes (100mL/hr). The bag will be labeled by the pharmacy as “Vitamin C 1.5g or Placebo”. The dosing schedule is 1500mg every 6 hours for 4 days (or discontinued earlier if discharged from the ICU).

Once the vial is open, it is only stable for 6 hours. The resulting product is given 12 hour stability. When first ordered, 2 doses are made then and sent to the nurse. For next 12 hours, they will wait until 1 hour prior to make the next batch.

Vitamin C placebo will consist of an identical bag of 50mL normal saline (but with no vitamin C) and will be labeled “Vitamin C or Placebo”. Placebo will be infused over 30 minutes as per the infusion instructions of the active vitamin.

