***Data Collection:***

The following de-identified demographic and clinical data will be collected.

- i. Age
- ii. Sex
- iii. Weight
- iv. Admitting diagnosis and possible site of infection
- v. Blood culture results
- vi. Co-morbidities, including diabetes, hypertension, cardiac failure, COPD, malignancy
- vii. Requirement for mechanical ventilation (Y/N).
- viii. Use of vasopressor agents (Y/N). The hourly dosage of vasopressors will be recorded as the norepinephrine equivalent dosage. [70,71]
- ix. Duration of vasopressor use
- x. Time to vasopressor independence from start of active drug/placebo
- xi. Daily urine output (for first 4 days)

xii. Fluid balance after 24 and 72 hours

xiii. Presence of acute kidney injury (AKI). Presence of AKI: Acute kidney injury (AKI) will be defined using the KDIGO criteria; namely, an increase of the s-creatinine > 0.3 mg/dl or a level > 1.5 times the baseline value. [27] If the baseline s-creatinine is not known a value > 1.5 mg/dl will be regarded as diagnostic of AKI.

xiv. Length of ICU and hospital stay

xv. ICU, hospital, and 28-day mortality

xvi. Routine laboratory data for 4 days including:

a. serum creatinine

b. white cell count (WBC)

c. platelet count

d. total bilirubin

e. PaO2/FiO2 ratio

f. Procalcitonin (PCT) – on days 1 and 4

g. lactate level

h. urine oxalate level (day 4)

xvii. HostDx Sepsis genetic testing (day 1) if consent is provided for additional sub-study.

xviii. The patients' admission APACHE II and APACHE IV scores will be recorded. The APACHE IV score allows calculation of the predicted hospital mortality and predicted ICU length of stay (LOS).

ix. The daily SOFA (Sepsis-related Organ Failure Assessment) score will be recorded for the first 4 treatment days.

The APACHE II score (incrementing score of 0-71) and APACHE IV score (incrementing score 0-286) are standardized measures of disease severity that are used to predict hospital mortality and ICU LOS.

[72,73] The SOFA score was designed to sequentially assess the severity of organ dysfunction in patients who are critically ill from sepsis (incrementing score 0-24). [74]. The SOFA scores is calculated 24 hours

after admission to the ICU and daily thereafter. SOFA scores that increase by about 30 percent are associated with a mortality of at least 50 percent.[75]

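### No renal safety comparison is pre-specified, and AKI as defined counts kidney injury present before the first dose, which dilutes any between-arm difference

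*Protocol*

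**What the plan says.** **Risk statements.** Under Data Safety & storage, the protocol states: "The main risk to subjects is the accidental release of PHI". The Background says that, in patients with renal impairment given mega-dose vitamin C, "supersaturation of serum with oxalate may result in tissue deposition as well as crystallization in the kidney". It also gives, as the only reported restriction on high-dose intravenous vitamin C, known "glucose-6-phosphate deficiency (G6PD) in whom hemolysis has been reported". Of the trial's own vitamin C dose, Medication dosing says: "This dosage is reported to be devoid of any complications or side effects".

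**Who can enter.** The exclusion criteria remove patients with known G6PD deficiency. They contain no renal criterion.

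**End-points.** The two primary end-points are time to vasopressor independence and delta SOFA. The secondary end-points are 28-day, hospital and ICU mortality, PCT clearance, ICU stay and ICU-free days, and hospital stay. The SAP repeats this list. Neither document lists AKI, urine oxalate or adverse events as an outcome.

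**What is collected.** Data Collection includes serum creatinine for 4 days, urine oxalate on day 4 only, and presence of AKI. AKI is a creatinine rise of more than 0.3 mg/dl or a level above 1.5 times baseline. It adds: "If the baseline s-creatinine is not known a value > 1.5 mg/dl will be regarded as diagnostic of AKI". The baseline value is not defined, and no window for the AKI is given.

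**Analysis.** Data analysis, in both documents, names two-group tests for comparing the arms but does not say which variables they apply to.

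**The concern.** The sponsor describes a renal mechanism and measures its markers, but commits to no comparison of them. Followed as written, the trial could report efficacy with no renal result.

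If an AKI comparison were made, the definition would work against it. A patient who arrives with raised creatinine and no known baseline is an AKI case before any study drug is given. So is a patient whose creatinine has already risen above a known pre-illness value. Randomisation balances such patients between arms on average, but it does not remove them. They add the same amount to both arms and shrink the difference in what happens after dosing. For a safety outcome that is the unfavourable direction, because a real excess looks smaller than it is and a null result reassures more than it should.

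**Working it through.** The plan gives no AKI rate, no oxalate distribution and no power figure for any safety outcome, so there is no figure of its own to reproduce. What follows is an illustration.

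**Inputs**
- From Power Calculation: target of 140 patients and alpha 0.05.
- Assumed, not in the documents: 1:1 allocation (70 per arm), two-sided testing, a fraction f with AKI at entry that is equal in both arms and counted in full, new-AKI risk p among the rest, and no treatment effect on the status of those already counted.

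**Step 1: what presence of AKI would show.** Observed rate = f + (1 − f)p, so the observed difference is (1 − f) times the true difference among those at risk.
- 35% v 15%, f = 0.30: 0.30 + 0.70 × 0.35 = 0.545 and 0.30 + 0.70 × 0.15 = 0.405. The 20-point gap becomes 14.
- 35% v 15%, f = 0.50: 0.675 and 0.575. The gap becomes 10.
- 25% v 15%, f = 0.30: 0.475 and 0.405. A 10-point gap becomes 7.
- 25% v 15%, f = 0.50: 0.625 and 0.575. The gap becomes 5.

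**Step 2: power.** With h = 2·arcsin√p₁ − 2·arcsin√p₂, power = Φ(|h|·√(n/2) − 1.96). Presence of AKI uses n = 70 per arm. New AKI uses only those at risk, n = 70(1 − f), which is 49 or 35.

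| New AKI, active v placebo | AKI at entry | Presence of AKI, n = 70 | New AKI in those at risk |
|---|---|---|---|
| 35% v 15% | 30% | 54.5% v 40.5%: h = 0.281, power 0.38 | n = 49: h = 0.471, power 0.64 |
| 35% v 15% | 50% | 67.5% v 57.5%: h = 0.207, power 0.23 | n = 35: h = 0.471, power 0.50 |
| 25% v 15% | 30% | 47.5% v 40.5%: h = 0.141, power 0.13 | n = 49: h = 0.252, power 0.24 |
| 25% v 15% | 50% | 62.5% v 57.5%: h = 0.102, power 0.09 | n = 35: h = 0.252, power 0.18 |

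**Step 3: what a confidence interval would show at f = 0.30.** Half-width = 1.96·√[(p₁(1 − p₁) + p₂(1 − p₂))/n].
- Presence of AKI, 54.5% v 40.5%: 1.96·√[(0.2480 + 0.2410)/70] = 0.164, giving 14 ± 16 points.
- New AKI, 35% v 15%: 1.96·√[(0.2275 + 0.1275)/49] = 0.167, giving 20 ± 17 points.
- New AKI, 25% v 15%: 1.96·√[(0.1875 + 0.1275)/49] = 0.157, giving 10 ± 16 points.

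At f = 0.30 the intervals are about equally wide for both outcomes. What changes is that the estimate is no longer shrunk.

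**Limit of the check.** The calculation covers new AKI in patients without AKI at entry. It does not cover the new-or-worsened outcome recommended below, which would need a further assumption about worsening in patients who enter with impaired kidneys.

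**The case against.** Several stronger readings are tempting, and the documents do not support them.

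- **The trial cannot conclude on renal harm.** It is randomised, double-blind and placebo-controlled, it collects AKI and creatinine, and Data analysis permits a between-arm test. A large difference could be seen. The comparison is unnamed, unpowered and, on the stated definition, diluted; it is not impossible.
- **The plan foresees this harm at its own dose.** The Background ties oxalate deposition to mega-dose vitamin C in renal impairment, and Medication dosing says the trial dose is reported free of complications. The Background also cites a post-hoc finding that thiamine lowered the risk of AKI. The plan describes a mechanism and measures its markers; it does not predict the injury.
- **Haemolysis is ignored.** Known G6PD deficiency is an exclusion criterion.
- **The PHI sentence shows that treatment risk was never considered.** It stands in a section otherwise about records, and it governs no analysis. Consent pages are not in the supplied text, so their risk wording cannot be checked.
- **Adverse events are not collected.** No such field appears in the supplied text, but Appendix A, the data spreadsheet, was not supplied and might contain one, or AKI timing.

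Two further objections have force. Mortality and delta SOFA carry some safety information, although neither isolates kidney injury after the first dose. The 20-point excess is also a large assumed effect. At 10 points power is low under either definition, so a better definition does not make the trial adequate to test renal safety. What survives is that no renal comparison is committed to and that the stated definition shrinks whatever difference exists.

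**Conclusion.** The point holds in this form: neither document pre-specifies a renal safety comparison, and AKI as defined in Data Collection mixes pre-treatment kidney disease with events after dosing. The size depends on assumptions. With 30% affected at entry, a true 20-point excess among those at risk would read as 14 points, and power falls from 0.64 to 0.38. A true 10-point excess would read as 7 points, with power 0.24 against 0.13. The dilution factor, 1 − f, holds for any event rates provided the entry fraction is equal between arms and entry cases are counted in full. The rates, the entry fraction and 1:1 allocation are not in the documents.

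The benefit of changing the definition is an undiluted estimate with an honest interval. It is not adequate power, and a null result would still leave a 10-point excess open. This is a change that should be made; it does not invalidate the efficacy comparison.

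**What to change.** 1. **Name the outcome.** In the protocol's secondary end-points and Data Collection, and in the SAP, add as a safety outcome new or worsened AKI from first dose to day 4. Apply the protocol's existing creatinine criteria against the last creatinine before the first dose, in all randomised patients. Show separately new AKI in those without AKI at entry, and results by renal status at entry, since the Background places the oxalate risk in patients with renal impairment.
2. **Report an estimate.** Give the risk difference with a 95% CI, not only a p-value.
3. **Urine oxalate.** Report the day-4 value by arm as supportive only. State that there is no baseline sample and that, because dosing stops at ICU discharge, values may be missing or taken off treatment.
4. **Adverse events.** Tabulate them by arm, and confirm that the data sheet has a field for them.
5. **Risk sentence.** Reconcile the statement in Data Safety & storage with the treatment risks described in the Background.

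**Cost:** wording in the protocol and SAP, a small analysis using creatinine and oxalate already planned, and possibly one adverse-event field on the data sheet.

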Outcomes of Metabolic Resuscitation Using Ascorbic Acid, Thiamine, and Glucocorticoids in the Early Treatment of Sepsis.

ORANGES Trial

NCT#: NCT03422159

Document Date: May 13th, 2019

Study end-points:

Primary end-point

- i. Time to vasopressor independence. Defined as the time from starting the active treatment/placebo to discontinuation of all pressors
- ii. Delta SOFA score, defined as the initial SOFA score minus the day 4 SOFA score

Secondary end-points

- iii. 28-day mortality
- iv. Hospital mortality
- v. PCT clearance (PCT-c) calculated using the following formula: initial PCT minus PCT at 96 hours, divided by the initial PCT multiplied by 100. [67,68]
- vi. ICU mortality
- vii. ICU length of stay (LOS) and ICU free days. ICU free days is calculated as the number of days alive and out of the ICU to day 28
- viii. Hospital LOS

Power Calculation:

Based on the results of the preliminary study of Marik et al we project that the combination of hydrocortisone, vitamin C and thiamine could reduce time to vasopressor discontinuation from 54 (+/- 30 hours) versus 30 hours. For the additional primary outcome we projected a greater change of SOFA

score of 4 (+/- 3) versus 2. Assuming a type 1 error of 5% (alpha of 0.05) and a power of 80% (the ability to detect a difference between two groups when a difference exists) would require a sample size of 94 patients. To account for dropouts and patients not requiring vasopressor therapy we will therefore aim for a sample size of 140 patients.

Data analysis:

Summary statistics will be used to describe the clinical data and presented as mean \pm SD, median with interquartile range (IQR) or percentages as appropriate. Chi squared analysis with Fisher's exact test (when appropriate) and Student's t test (Mann Whiney U test for non- normal distributions) were used to compare data between the active treatment group and the placebo group with statistical significance declared for probability values of 0.05 or less.
